Abnormal laboratory values or clinical findings for all enrolled subjects after dosing will be assessed using the toxicity scales in [Appendix C](#). Abnormal values and findings noted at screening or baseline will only be considered AEs if they deteriorate after study drug dosing. For abnormalities noted from the time of first study drug dosing, any Grade 1 or higher laboratory abnormality listed on the toxicity table in [Appendix C](#) will be entered in the database as an AE. Safety laboratory results that are abnormal according to the local laboratory reference range, but not considered Grade 1 abnormalities, will be evaluated by the CTU clinician and reported as Grade 1 abnormalities if clinically significant. If not clinically significant, these will not be considered laboratory AEs and thus will not be graded but will be recorded in the source document and followed-up clinically at the discretion of the CTU clinician. Abnormal laboratory

values, performed as part of HEM, CHEM, or UA but not listed in this toxicity table will be evaluated by the study clinicians, recorded in the source document and, if clinically significant, considered AEs and graded according to the criteria in [Section 9.2.1](#).

Protocol-specific laboratory normal range values in effect at the time of protocol submission are included in [Appendix B](#). Changes in these ranges during the trial will be handled as administrative protocol amendments and toxicity grades will be calculated using the new ranges from the effective date of the change. A regular protocol amendment will be submitted for these changes if a revised laboratory normal range value meets criteria for Grade 2 toxicity.

Gross blood in urine that is confirmed due to menses is not an AE (but is for all other reasons).

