Appendix B: Acceptable Ranges of Screening Laboratory and Vital Sign Measurements

Table 4: Acceptable Ranges of Screening Laboratory and Vital Sign Measurements – Hematology and Chemistry

HEMATOLOGY AND CHEMISTRY				
Lab test name	Reference range	Acceptable lower limit	Acceptable upper limit	Lab unit
Hemoglobin (Hgb), male	13.2 - 17.1	13.0	18.5	g/dL
Hemoglobin (Hgb), female	11.7 – 15.5	11.3	16.5	g/dL
Hematocrit (Hct), male	38.5 – 50.0	38.5	54	%
Hematocrit (Hct), female	35 - 45	35	49	%
White blood cell count (WBC)	3,800 – 10,800	3,500	11,500	cells/ μ L
Neutrophil count	1,500 – 7,800	1,200	8,500	cells/ μ L
Lymphocyte count	850 – 3,900	800	5,000	cells/ μ L
Monocyte count	200 - 950	0	1,100	cells/ μ L
Eosinophil count	150 - 500	0	600	cells/ μ L
Basophil count	0-200	0	300	cells/ μ L
Platelet count	140 - 400	125	475	$10^3/\mu$ L
Sodium	135 - 146	132	148	mmol/L
Potassium	3.5 - 5.3	3.3	5.5	mmol/L
CO ₂ (Bicarbonate)	20 - 32	19	33	mmol/L
Chloride	98 -110	94	115	mmol/L
Calcium	8.6 - 10.3	8.0	11.0	mg/dL
Magnesium	1.5 - 2.5	1.1	2.8	mg/dL
Blood urea nitrogen (BUN)	7 – 25	0	28	mg/dL
Glucose, fasting	65 - 99	50	115	mg/dL
Serum creatinine, male	0.6 – 1.35	0.5	1.45	mg/dL
Serum creatinine, female	0.5 – 1.10	0.4	1.2	mg/dL
Direct bilirubin	0.0-0.2	0	0.4	mg/dL
Total bilirubin	0.2 – 1.2	0	1.4	mg/dL
Total protein	6.1 - 8.1	5.8	8.6	g/dL
Albumin	3.6 – 5.1	3.2	6.0	g/dL
Aspartate transferase (AST), male	10 - 40	0	45	U/L
Aspartate transferase (AST), female	10 - 30	0	35	U/L
Alanine transferase (ALT), male	9 - 46	0	52	U/L
Alanine transferase (ALT), female	5 - 32	0	38	U/L
Alkaline phosphatase, males	40 - 115	0	150	U/L
Alkaline phosphatase, females	33 – 115	0	150	U/L
Hepatitis B surface antigen (HBsAg)	non-reactive	non-reactive	non-reactive	n/a
Hepatitis C antibody (HCVAb)	non-reactive	non-reactive	non-reactive	n/as
HIV-1/ HIV-2 antibody	non-reactive	non-reactive	non-reactive	n/a

Serum β -HCG (females only)	negative	negative	negative	n/a
FSH (post-menopausal females only)	23 – 116.3	23	116.3	mIU/mL

Footnotes: Exceptions to screening laboratory tests' normal reference ranges are:

- a. Racially-based low total WBC or neutrophil counts up to toxicity Grade 1 in [Appendix C](#) Toxicity Tables are allowed, but toxicity Grades 2 or 3 are exclusionary.

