Mucocutaneous	Erythema, pruritus	Diffuse, maculopapular rash, dry desquamation	Vesiculation OR moist desquamation OR ulceration	
Pruritus	No or minimal interference with usual social and functional activities	Greater than minimal interference with usual social and functional activities	Inability to perform usual social and functional daily activities	
ALL OTHER CONDITIONS				
Illness or clinical AE (as defined according to applicable regulations)	Require minimal or no treatment; does not interfere with the subject's daily activities.	Result in a low level of inconvenience or concern with therapeutic measures; may cause some interference with functioning.	Interrupt a subject's usual daily activity and may require systemic drug therapy or other treatment; are usually incapacitating	

Table 8: Toxicity Grading Tables – Laboratory AEs

Laboratory AEs	Mild (Grade 1)	Moderate (Grade 2)	Severe (Grade 3)
Blood, serum, or plasma *			
Sodium decrease – mmol/L	130 - 131	125 –129	<125
Sodium increase – mmol/L	149 - 150	151 – 153	>153
Potassium increase – mmol/L	5.6 – 6.0	6.1 – 6.4	≥6.5
Potassium decrease – mmol/L	3.0 – 3.2	2.5 – 2.9	<2.5
Bicarbonate (CO ₂) increase – mmol/L	34 - 35	36 - 37	>37
Bicarbonate (CO ₂) decrease – mmol/L	17 - 18	14 - 16	<14
Glucose decrease, fasting – mg/dL	47 - 49	45 –46	<45
Glucose increase, fasting – mg/dL	116 – 125	126 – 249	≥250
Glucose increase, non-fasting – mg/dL	116 – 160	161 – 249	≥250
Blood urea nitrogen – mg/dL	25 - 27	28 – 32	>32
Creatinine increase, male – mg/dL	1.46 – 1.7	1.71 – 2.3	>2.3
Creatinine increase, female – mg/dL	1.21 – 1.5	1.51 – 2.0	>2.0
Calcium decrease – mg/dL	7.8 – 8.0	7.0 – 7.7	<7.0
Calcium increase – mg/dL	11.0 – 11.4	11.5 – 12.4	≥12.5
Total protein decrease – g/dL	5.1 – 5.7	4.6 – 5.0	<4.6
Albumin decrease – g/dL	2.8 – 3.4	2.5 – 2.7	<2.5
AST increase, male – U/L	46 – 115	116 – 220	>220
AST increase, female – U/L	36 - 90	91 - 175	>175
ALT increase, male – U/L	53 – 115	116 - 230	>230
ALT increase, female – U/L	39 – 95	96 – 190	>190
Alkaline phosphatase increase – U/L	151 – 240	241 – 360	>360
Total bilirubin (serum) increase – mg/dL (with other LFTs in the normal range)	1.5 – 2.0	2.1 – 2.5	>2.5
Total bilirubin (serum) increase – mg/dL (accompanied by a >3 x ULN increase in ALT or AST)**	1.5 – 1.7	1.8 – 2.1	>2.1
Hemoglobin decrease, female – g/dL	10.8 – 11.2	9.4 – 10.7	<9.4
Hemoglobin decrease, male – g/dL	11.8 – 12.9	10.0 – 11.7	<10.0
WBC increase – cells/μL	11,000 – 15,000	15,001 – 20,000	>20,000

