WBC decrease – cells/μL	2,500 – 3,500	1,500 – 2,499	<1,500
Neutrophils decrease – cells/μL	1,200 – 1,499	1,000 – 1,199	<1,000
Lymphocytes decrease – cells/μL	750 – 849	500 – 749	<500

Laboratory AEs	Mild (Grade 1)	Moderate (Grade 2)	Severe (Grade 3)
Monocytes increase – cells/μL	1,101 – 2,000	2,001 – 3000	>3,000
Eosinophils increase – cells/μL	500 – 750	751 – 1,500	>1,500
Basophils increase – cells/μL	201 – 500	501 – 800	>800
Platelets decrease – cells/μL	120,000 – 124,000	100,000 – 119,000	<100,000
Urine*			
Protein	1+	2+	>2+
Glucose	1+	2+	>2+
Blood (dipstick)	1+	2+	>2+
Blood (microscopic) – RBCs per HPF	6-10	11-50	>50 and/or gross blood
WBC (microscopic) – WBC per HPF	6-10	11-50	>50
Bacteria (microscopic)	few	moderate	many

* Institutional normal reference ranges and allowable ranges at screening are provided in [Appendix B](#).

**ALT, males: >216 U/mL; ALT, females: >132 U/mL; AST, male or female: >126 U/mL)

Note 1: If a subject was accepted into the trial with a laboratory value of an analyte that overlaps with values used for grading Grade 1 laboratory abnormalities, an AE will be reported if the on-study value of the same analyte is different (worse) from the baseline.

Note 2: Safety laboratory results that are abnormal according to the local laboratory reference range, but not considered a Grade 1 abnormality, will be evaluated by the CTU clinician and reported as Grade 1 abnormalities if clinically significant. If not clinically significant, these will not be considered laboratory AEs and will thus not be graded but will be recorded in the source document and followed-up clinically at the discretion of the CTU clinician.

Note 3: Other laboratory parameters performed and reported as part of the CBC, metabolic panel, and UA will be evaluated by the study clinician, recorded in the source document, reported as laboratory AEs if clinically significant, and graded according to the criteria in [Section 9.2.1](#).

Note 4: If the dipstick UA is abnormal, a microscopic UA will be performed, and the results will supersede the results of the dipstick UA.

Note 5: Menstruating females with a positive dipstick UA or microscopic UA may be retested following cessation of menses.

Table 9: Toxicity Grading Tables – ECG

ECG interval abnormality	Grade 1	Grade 2	Grade 3

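### Protocol Table 8's figures for three times the ULN do not match Appendix B, and its two bilirubin rows leave a band of ALT and AST values with no bilirubin grade

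*Protocol*

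**What the plan says.** Protocol Appendix C, Table 8 has two rows for a rise in total bilirubin.

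- The first applies "with other LFTs in the normal range": Grade 1 is 1.5-2.0, Grade 2 is 2.1-2.5 and Grade 3 is >2.5 mg/dL.
- The second applies when the rise is "accompanied by a >3 x ULN increase in ALT or AST": Grade 1 is 1.5-1.7, Grade 2 is 1.8-2.1 and Grade 3 is >2.1 mg/dL. Its ** footnote reads "ALT, males: >216 U/mL; ALT, females: >132 U/mL; AST, male or female: >126 U/mL".

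The same table's * footnote sends the reader to Appendix B for normal ranges, and section 9.2.3 agrees: "Protocol-specific laboratory normal range values in effect at the time of protocol submission are included in" Appendix B. In Appendix B, Table 4, the row "Alanine transferase (ALT), male" has a reference range ending at 46 U/L (women 32), and "Aspartate transferase (AST), male" has one ending at 40 U/L (women 30).

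For results outside the reference range that reach no Grade 1 limit, Table 8 Note 2 has the site clinician decide, with the result "reported as Grade 1 abnormalities if clinically significant".

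SAP Table 4 repeats both bilirubin rows and the ** marker, but no footnote text follows. SAP section 9 gives a result a grade only when it meets the table criteria and is worse than baseline. SAP section 9.6 flags other out-of-range results as ONR.

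**The concern.** A threshold described as three times the ULN should equal three times the ULN that the protocol names. If it does not, a site reading the row and a site reading the footnote will grade the same blood sample differently, and a programmer working from the SAP, which has only the row, may differ from the site.

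The second problem is independent of those numbers. The two conditions are not complements: one requires normal liver tests, the other a threefold elevation. A mild or moderate transaminase rise fits neither.

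Grade has consequences. Under section 7.3 a related Grade 3 AE means withdrawal, and a Grade 2 AE must resolve or fall to Grade 1 before the next dose. Under section 9.5.1, related Grade 3 systemic AEs in one organ system count towards halting. Bilirubin rising together with transaminases is also the pattern that the second row was written to grade more strictly.

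**Working it through.** **Step 1. The footnote against Appendix B.** Inputs are the reference-range upper limits in Appendix B, Table 4 (U/L) and the footnote cut-offs. Formulas: threshold = 3 x ULN; implied ULN = footnote / 3; excess = footnote / (3 x ULN) - 1.

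| | ULN | 3 x ULN | Footnote | Implied ULN | Footnote / ULN | Excess |
|---|---|---|---|---|---|---|
| ALT, men | 46 | 138 | 216 | 72 | 4.70 | 57% |
| ALT, women | 32 | 96 | 132 | 44 | 4.13 | 38% |
| AST, men | 40 | 120 | 126 | 42 | 3.15 | 5% |
| AST, women | 30 | 90 | 126 | 42 | 4.20 | 40% |

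No other limit in the documents reproduces the footnote. Three times the Appendix B acceptable upper limits (ALT 52 / 38, AST 45 / 35) gives 156, 114, 135 and 105. Three times the lower bound of Grade 1 in Table 8 (53 / 39, 46 / 36) gives 159, 117, 138 and 108. The footnote also uses one AST limit for both sexes where Appendix B has two. It prints U/mL where both tables use U/L; read literally, that is a factor of 1000.

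**Step 2. Where row and footnote disagree.** These are the whole-number values above 3 x ULN but not above the footnote: ALT 139-216 (men) / 97-132 (women), AST 121-126 (men) / 91-126 (women). Example: a man with ALT 150, AST 60 U/L and bilirubin 2.3 mg/dL. By the row text, 150 > 138, so the second row applies and 2.3 > 2.1 is Grade 3. By the footnote, 150 is not above 216 and 60 is not above 126, so the second row does not apply. The first row does not apply either, because his transaminases are not normal.

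**Step 3. The gap, using the correct 3 x ULN.** Neither row applies for ALT 47-138 (men) / 33-96 (women) or AST 41-120 (men) / 31-90 (women), provided the other transaminase is also not above 3 x ULN. Take a man with AST 35 and alkaline phosphatase 80 U/L and bilirubin 3.0 mg/dL:

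- ALT 46: first row, Grade 3.
- ALT 50: neither row, no grade. ALT itself has no grade below 53, so both results are flagged only ONR.
- ALT 150: second row, Grade 3.

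The grade disappears as ALT rises and then returns. Values of ALT 47-52 / 33-38 and AST 41-45 / 31-35 are acceptable at screening, so an eligible subject can enter the trial already outside the first row. The protocol does not define which tests count as other LFTs. If alkaline phosphatase counts, a value of 116-150 U/L (normal to 115, own Grade 1 from 151) has the same effect even with normal transaminases.

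**Step 4. What the SAP does with such a value.** It meets no criterion, so it is flagged ONR, is left out of SAP Table 17 (graded results only) and is not counted in any grade in SAP Table 20. It remains in Table 21, Figure 27 and Listing 9.

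**Step 5. Two smaller mismatches.** Urine WBC Grade 1 starts at 5 in SAP Table 4 but at 6 in Protocol Table 8, and 5 is within the Appendix B range of 0-5. SAP Table 3 drops the baseline >60 condition that Protocol Table 7 attaches to the first set of bradycardia limits.

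**The case against.** The strongest reply is that little depends on this. The footnote numbers are not printed in the SAP, so a programmer following SAP Table 4 can apply the row text and grade the Step 2 example as Grade 3. That stands: the wrong numbers mainly affect grading at the site. It also means that the report could show a grade that the site did not use.

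A reader might infer that a bilirubin in the gap escapes all control over further dosing. The documents do not support that. Note 2 calls for clinician review. The generic mild/moderate/severe scale in Appendix C arguably applies, although it is meant for abnormalities not found in the tables and has no numeric limits. Section 7.3 asks for the investigator's judgement, and section 5.3.3 allows removal for well-being or for an AE warranting withdrawal. A value reported as an AE also appears in SAP Tables 13 and 14 and Listing 8, and in Table 16 if it is non-serious and moderate or severe. None of these supplies a numeric grade that can be programmed.

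A reader might also argue that fixed footnote numbers cannot follow a change of reference range, since "toxicity grades will be calculated using the new ranges from the effective date of the change". That is weak: section 9.2.3 handles such changes by administrative amendment, and nearly every cut-off in Table 8 is a fixed number.

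The ALT 50 example depends on taking normal to mean the reference range. If normal meant the acceptable screening limits, the gap would start at ALT 53 / 39 and AST 46 / 36, and every remaining case would have a transaminase graded in its own row when worse than baseline. The gap would be narrower but still there, and Table 8's * footnote distinguishes reference ranges from allowable ranges.

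Finally, one might read SAP Table 3 as giving two grades to the same heart rate when baseline is below 60 (45-49 in Grades 1 and 2, 40-44 in Grades 2 and 3). That needs a very literal reading. The natural one is that the second range replaces the first.

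**Conclusion.** The point holds as a wrong threshold and an incomplete grading rule, and it should be corrected. The footnote exceeds three times the Appendix B ULN by 57%, 38%, 5% and 40% (ALT men, ALT women, AST men, AST women). It makes row and footnote disagree in the bands in Step 2. The two bilirubin rows leave the Step 3 bands without a numeric grade in either document.

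This rests on the Appendix B reference ranges being those in effect, as section 9.2.3 states, and for the lower edge of the gap on normal meaning the reference range. It concerns safety grading only. The QTcF analysis and the sample size are untouched. No expected number of cases is claimed; in screened healthy adults such combinations should be rare.

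**What to change.** - In Protocol Table 8 and SAP Table 4, replace the footnote numbers with three times the Appendix B ULN in effect (currently ALT 138 / 96 and AST 120 / 90 U/L, men / women).
- In both tables, reword the first bilirubin row to apply whenever neither ALT nor AST exceeds that threshold. The two rows then cover every case, and the undefined set of other liver tests no longer matters. In men, ALT 50 with bilirubin 3.0 becomes Grade 3, ALT 100 with 2.3 becomes Grade 2, and ALT 150 with 2.3 stays Grade 3 (AST not above 120 in the first two).
- As minor alignment, start SAP urine WBC Grade 1 at 6, and restore the baseline condition in the SAP bradycardia row. Write it as baseline >=60 versus <60 in both documents, because the protocol's >60 and <60 omit exactly 60.

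The cost is small: a correction to Protocol Appendix C (Tables 7 and 8) and SAP Tables 3 and 4, and a minor change to the grading program. No design change or new data collection is needed.

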Appendix D: Blood Volume Withdrawn During the Trial

Table 10: Laboratory Samples and Estimated Total Blood Volume (mL)

Study Periods	Inpatient Periods 1 to 4				Outpatient Periods 1 - 4	Dosing Period 4	ET
Study Visit	Screen	Check-in	Dosing	Follow-up	Wash-out	Final	
+Study Day ^a	-21 to -2	-1	1	2	3-7	8 (±2)	
+							
HEMATOLOGY ¹	4	4		4		4	4
CHEMISTRY and serum β-HCG and FSH ¹	5	5		5		5	5
Viral Serology (HIV, HBsAg, HCV) ¹	8.5						
PK ³			54	6			6
Total volume/visit	17.5	9	54	15	0	9	15
Dosing periods multiplier	1	4	4	4		1	1
Total volume (all dosing periods)	17.5	36	216	60	0	9	15
Cumulative total volume	17.5	53.5	269.5	329.5	329.5	338.5	

^a Study Days shown correspond to days in each treatment period. For a view of the cumulative numbering of study days, please refer to [Section 7](#).

¹ Clinical blood tests (HEM, CHEM) are drawn at Screening Visit, on Day -1, and on Day 2 in each treatment period, or ET. Serum pregnancy test in all women at Screening and within 24 h before each dosing period, and at the Final Visit, or ET. FSH only at Screening in post-menopausal women.

² Viral serology tests are drawn at Screening.

³ PK serum samples are drawn on Day 1: 30 min before dosing and at 0.5, 1, 2, 3, 4, 6, 8, 12, and 24 h after dosing in each dosing period, or ET if occurs within 24 h of dosing.

Appendix E: A Partial List of Drugs Causing QTc Prolongation and Torsade de Pointes

Table 11: A Partial List of Drugs Causing QTc Prolongation and Torsade de Pointes

CATEGORY	DRUG
Anti-arrhythmic agents	Amiodarone Disopyramide Dofetilide Dronedarone Flecainide Ibutilide Procainamide Quinidine Sotalol
Anti-infective agents	Azithromycin Ciprofloxacin Clarithromycin Erythromycin Levofloxacin Moxifloxacin
Anti-malarial agents	Chloroquine
Anti-psychotic agents	Chlorpromazine Droperidol Haloperidol Pimozide Thioridazine
Anesthetics, General	Propofol Sevoflurane
Others	Methadone Papaverine HCl

Source: <https://crediblemeds.org/> (accessed 19 December 2017) and Reference 17

APPENDIX 2. FIGURE MOCK-UPS90

APPENDIX 3. LISTINGS MOCK-UPS.....115

LIST OF ABBREVIATIONS

AE	Adverse Event
ALT	Alanine Aminotransferase
AP	Alkaline Phosphatase
AST	Aspartate Aminotransferase
ATC	Anatomical Therapeutic Code
AUC	Area Under the Curve
AUC _(0-inf)	AUC Extrapolated to Infinity
AUC _(0-last)	AUC from Time of Dosing to Time of the Last Measured Concentration.
AUC _(0-t)	AUC from Time of Dosing to Time t .
AV	Atrioventricular
BMI	Body Mass Index
bpm	Beat(s) per Minute
BQL	Below Quantification Limit
BUN	Blood Urea Nitrogen
C	Degree(s) Celsius
CDC	Centers for Disease Control and Prevention
CI	Confidence Interval
CL/F	Apparent Oral Clearance
C _{last}	Last Measured Concentration above the Lower Limit of Quantification
C _{max}	Maximum Concentration
CO ₂	Total Carbon Dioxide
CRF	Case Report Form
CS	Clinically Significant
CSR	Clinical Study Report
CTU	Clinical Trials Unit
CV	Coefficient of Variation
ΔΔQTcF	Time-Matched, Placebo-Corrected, Baseline-Adjusted Mean QTcF Interval
DCC	Data Coordinating Center
DMID	Division of Microbiology and Infectious Diseases
ECG	Electrocardiogram

List of Abbreviations *(continued)*

EDC	Electronic Data Capture
eGFR	Estimated Glomerular Filtration Rate
ET	Early Termination
FEV1	Forced Expiratory Volume in One Second
FDA	United States Food and Drug Administration
FSH	Follicle Stimulating Hormone
g	Gram(s)
GCP	Good Clinical Practice
GFR	Glomerular Filtration Rate
GM	Geometric Mean
GSD	Geometric Standard Deviation
h	Hour(s)
HBsAg	Hepatitis B Surface Antigen
hCG	Human Chorionic Gonadotropin
HCV	Hepatitis C Virus
HIV	Human Immunodeficiency Virus
HLGT	High Level Group Term
ICF	Informed Consent Form
ICH	International Council for Harmonisation of Technical Requirements for Pharmaceuticals for Human Use
ISM	Independent Safety Monitor
IUD	Intrauterine Device
K_e	Terminal Phase Elimination Rate Constant
LLOQ	Lower Limit of Quantification
LQTS	Long QT Syndrome
LVH	Left Ventricular Hypertrophy
MedDRA	Medical Dictionary for Regulatory Activities
max	Maximum Value
min	Minimum Value
mg	Milligram(s)
MH	Medical History
MI	Myocardial Infarction

List of Abbreviations *(continued)*

mL	Milliliter(s)
MOP	Manual of Procedures
msec	Millisecond(s)
N	Number (typically refers to subjects)
NCA	Noncompartmental Analysis
NCS	Not Clinically Significant
NIAID	National Institute of Allergy and Infectious Diseases
NIH	National Institutes of Health
NSAID	Nonsteroidal Anti-Inflammatory Drug
OCRR	Office of Clinical Research Resources
ONR	Outside Normal Range
OTC	Over-the-Counter
PD	Pharmacodynamic(s)
PE	Physical Examination
PI	Principle Investigator
PK	Pharmacokinetic(s)
PT	Preferred Term
QTcF	QT Interval of the ECG Corrected Using Fridericia's Formula
RBC	Red Blood Cell
SAE	Serious Adverse Event
SAP	Statistical Analysis Plan
SD	Standard Deviation
SDTM	Standard Data Tabulation Model
SMC	Safety Monitoring Committee
SOC	System Organ Class
$t_{1/2}$	Apparent Terminal Elimination Half-Life
TdP	Torsades de Pointes
TFLs	Tables, Figures, and Listings
TIA	Transient Ischemic Attack
T_{max}	Time to Obtain Maximum Concentration (C_{max})
TQT	Thorough QT/QTc

List of Abbreviations *(continued)*

V _z /F	Apparent Volume of Distribution During Terminal Phase
WBC	White Blood Cell
WHO	World Health Organization

1. PREFACE

The Statistical Analysis Plan (SAP) for “A Phase 1, Randomized, Double-Blinded, Four-Period Crossover, Thorough QT/QTc (TQT) Clinical Trial to Evaluate the Effect of Zoliflodacin on Cardiac Repolarization in Healthy Male and Female Subjects” (DMID Protocol 16-0110) describes and expands upon the statistical information presented in the protocol. This document describes all planned analyses and includes example tables, figures, and listings (TFLs) planned for all planned analyses. This SAP follows the International Council for Harmonisation (ICH) guidelines, including E9[1] and E14[2]. Within the TFL mock-ups (Appendices 1, 2, and 3), references to the clinical study report (CSR) sections are included. Any deviation from this SAP will be described and justified in the CSR. The main text of this SAP discusses analysis of safety and pharmacokinetic (PK) endpoints for the study. Analysis of Holter ECG endpoints is presented in the ECG SAP ([Appendix 4](#)).

